Cognitive impairments are present in up to 80% of homeless individuals, and may contribute to homelessness in OEF/OIF/OND Veterans. We propose to investigate these issues in homeless, treatment-seeking returning Veterans, who arguably face multiple potential barriers to recovery and reintegration, and with whom we have the greatest opportunity to prevent long-term homelessness. We plan to conduct a 15-week randomized controlled trial of an evidence-based, 10-week Compensatory Cognitive Training (CCT) intervention vs. an education control condition

connect), depending upon patients' preferences or if required in the wake of the coronavirus pandemic. We expect CCT-associated improvements in cognition and functional skills and generalization to reduced levels of disability, along with improved community reintegration outcomes. By attending to and treating cognitive impairments, we can potentially prevent future homelessness and its negative health consequences, resulting in both healthcare cost savings and improved quality of life for Veterans.

Section 6 - Specific Aims

6) Provide a statement of specific aims and hypotheses that serve as the basis for this protocol. Emphasize those aspects that justify the use of human subjects.

Aim 1. Investigate the efficacy of cognitive rehabilitation in homeless returning veterans with mental health conditions and cognitive impairment by conducting a randomized controlled trial of Compensatory Cognitive Training (CCT) vs. education control for 10 weeks, with a 5-week follow-up, followed by 1 year of monthly post-discharge follow-up phone calls to assess community reintegration outcomes.

H1a: Positive CCT-associated effects on cognition, functional capacity (co-primary outcomes), and disability will emerge over the 15-week study.

H1b: Positive CCT-associated effects on community reintegration outcomes (housing stability, participation in employment/education, healthcare appointment attendance) will be detected at the end of the 1-year follow-up.

Aim 2. Investigate mechanisms of CCT effects.

H2: Improved cognition and cognitive strategy use will mediate improvements in functional capacity, disability, and community reintegration.

Exploratory Aim 3. Investigate moderators of CCT effects.

Presence and severity of PTSD, depression, history of substance abuse, and TBI, as well as duration of homelessness and baseline cognitive functioning, will be explored as potential moderators of CCT effects.

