We have selected measures based on 4 criteria: 1) importance for assessing constructs in our theoretical model, 2) brevity (to reduce subject burden), 3) reliability, and 4) demonstrated validity.

Subject Characterization Measures

Measures of demographics, residential and vocational history, and history of alcohol and substance abuse will be administered by Aspire Center staff as part of the routine clinical intake process at program entry (Table 2). Subject characterization measures we will add (Table 3) include the Warrior Administered Retrospective Casualty Assessment Tool (WARCAT; Terrio et al., 2009), a short, structured interview of TBI history that allows for diagnosis of mild, moderate, or severe TBI based on the American Congress of Rehabilitation Medicine criteria, and the Wide Range Achievement Test-4 (Wilkinson et al., 2006) Reading subtest, which provides an estimate of premorbid IQ by measuring ability to read non-phonetically spelled English words.

Table 2. Measures Administered during Aspire Center Intake (no additional subject burden)

Measure	Construct Assessed
Demographic Form	Age, sex, education, race/ethnicity, marital status, service connection, medications prescribed
Residential Timeline Follow-Back (Tsemberis et al., 2007)	Residential history (number of days homeless, unstably housed, in an institution, or housed in the past 6 months)

Alcohol Use Disorders Identification Test (Saunders et al., 1993)	Alcohol use history
Drug Abuse Screening Test (Skinner, 1982)	Substance use history

Study Measures

Additional study measures are listed in Table 3 and further described below. Time required for these measures will be about 2 hours, 15 minutes, and breaks will be provided as needed by participants. We will administer a comprehensive, standardized battery at all four time points, including the following:

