Dependent variables: Proportion of months housed, proportion of months engaged in productive activity (work or school), and proportion of VA healthcare appointments attended during the 1-year follow up period (all three outcomes based on monthly data collected during the 1-year follow-up period). Any missing data on housing and work/school status will be accounted for by using a proportion based on the available data points. Healthcare appointment attendance will be gathered from CPRS data and will not be subject to missing data.

Independent variable: Treatment group (CCT vs education control).

Statistical analyses: ANOVA models comparing the treatment and control group on the three dependent variables above. We have selected ANOVA over alternative models (t-test; Wilcoxon Rank Sum; Poisson regression) due to the type of dependent variables (continuous) and the option to include any covariates that might be imbalanced between the treatment groups.

Power analysis: With 78 subjects (39 subjects per group), we will have .80 power to detect an effect size of .64, a medium-to-large effect size.

capacity, disability, and community reintegration.

Dependent variables: UPSA-B at 15 weeks, WHODAS 2.0 at 15 weeks, proportion of months housed, proportion of months engaged in productive activity (work or school), and proportion of VA healthcare appointments attended during the 1-year follow up period.

Independent variables: Treatment group (CCT vs education control).

Mediators: Cognitive improvement in GDS composite from 0-10 weeks (slope of change across weeks), improvement in CPSA cognitive strategy use from 0-10 weeks (slope of change across weeks).

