Statistical analyses: For this hypothesis, we will use the regression analytic strategy described by Krull and MacKinnon (1999, 2001). In this approach, four conditions must be met: a) a significant relationship between the independent variable (treatment group) and the dependent variables listed above, b) a significant relationship between the independent variable (treatment group) and the proposed mediators listed above, c) a significant relationship between the mediator and the dependent variables listed above, and d) the relationship between the independent variable (treatment group) and dependent variables listed above must be significantly lower after controlling for the proposed mediator. To test for significant mediation, we will conduct a Sobel test (Sobel, 1982). We will also use the formula provided by MacKinnon and Dwyer (1993) to determine the percentage of the intervention condition to primary outcome path that was accounted for by change in the mediator.

Power analysis: For the second hypothesis, we used the procedures defined by Fritz and MacKinnon (2007) for estimating sample sizes needed to achieve 80% power to detect the mediated effect. Similar to previous hypotheses, we have assumed a medium effect for the relationships between intervention condition and dependent variables and between mediators and our primary outcome. Using the Sobel test procedure described in our statistical analysis section above, we estimate that the proposed sample size would be sufficient to achieve 80% power to detect a mediated effect.

Exploratory Aim 3. Examine moderators of CCT effects.

Dependent variables: GDS composite, UPSA-B, WHODAS 2.0, proportion of months housed, proportion of months engaged in productive activity (work or school), and proportion of VA healthcare appointments attended during the 1-year follow up period.

Independent variable: Treatment group (CCT vs education control).

Moderators: Presence and severity of PTSD, depression, history of substance abuse, and TBI, duration of homelessness, baseline cognitive functioning (GDS composite)

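### The H2 mediation regressions for week-15 UPSA-B and WHODAS 2.0 prespecify no baseline covariate, which gives up precision and leaves baseline level as a potential confounder of the mediator-outcome path

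*Combined protocol and SAP*

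**What the plan says.** H2 in Section 6 (Specific Aims) is about change: "Improved cognition and cognitive strategy use will mediate improvements in functional capacity, disability, and community reintegration".

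The analytic plan in Section 9 then sets H2 up as follows.

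- **Outcomes:** "Dependent variables: UPSA-B at 15 weeks, WHODAS 2.0 at 15 weeks, proportion of months housed", plus the two other 1-year proportions. UPSA-B and WHODAS enter as end levels.
- **Listed regressor:** "Independent variables: Treatment group (CCT vs education control").
- **Mediators:** "Cognitive improvement in GDS composite from 0-10 weeks (slope of change across weeks"), and the same slope for CPSA strategy use.
- **Decision rule:** four conditions followed by a Sobel test. One condition is "a significant relationship between the mediator and the dependent variables listed above"; another is a significant treatment-outcome relationship. No covariate is named in any step.

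Baseline values exist. Under Study Measures: "We will administer a comprehensive, standardized battery at all four time points". The H1a model includes week 0.

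Elsewhere, covariates appear only as a response to differences between the randomised groups: alcohol history under the eligibility criteria, the general statement in Design Considerations, and the H1b ANOVA.

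**The concern.** Randomisation protects the effect of arm on the mediator and of arm on the outcome. It does not protect the effect of the mediator on the outcome. If participants who start with poorer function also gain more, or less, in cognition, an unadjusted regression of the week-15 level on the mediator slope mixes that starting difference into the mediator path. This can happen within each arm even when the arms are perfectly balanced, so the imbalance rules do not address it.

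The second loss is precision. The plan justifies its H1a mixed model partly by its power advantage over end-point analysis, yet H2 uses an end-point regression for UPSA-B and WHODAS. Two of the four conditions, the treatment-outcome and mediator-outcome relationships, are tested with more residual variance than necessary.

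**Working it through.** **Inputs from the documents.** Final sample 78, 39 per group; correlation between time points .5 (H1a power analysis); H1b detectable effect .64 at .80 power.

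**Assumptions.** Two-sided alpha .05 for H2 (Bonferroni is named only for H1a and H1b). The .5 applies from baseline to week 15. Arm-to-mediator effect d = .64 or .72; these are the plan's H1b and H1a effect sizes, borrowed because H2 says only that effects are medium. Mediator path .39, which is not in the documents. All variables are coded so that higher is better.

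**1. The plan's nearest figure.** A two-sample t-test with 39 per group and d = .64 has power .797, so the H1b figure reproduces. H2's own 80% cannot be reproduced, because no path values are given.

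**2. Precision of the arm comparison.** Residual variance factor 1 − r² = 1 − .25 = .75. Effective size 78/.75 = 104. Detectable d goes from .64 to .64 × √.75 = .55. If r were .3 or .8, 78 would act like 78/.91 = 86 or 78/.36 = 217.

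**3. Precision of the mediator path.** Model: M = effect of arm + error; Y15 = .39·M + .5·Y0 + error with variance .75; Y0 unrelated to M.

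- Unadjusted SE ≈ √(1/75) = .115.
- Adjusted for Y0, SE ≈ √(.75/74) = .101.
- Simulated Sobel power: about .55 to .64 (d = .64) and .65 to .73 (d = .72).

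**4. The full decision rule.** In this model arm acts on the outcome only through the mediator, so the total effect is small: .64 × .39 = .25 or .72 × .39 = .28. A significant Sobel test together with a significant treatment-outcome relationship occurs in only about 11% of runs unadjusted and 16% adjusted (d = .64), or 15% and 20% (d = .72).

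**5. Potential confounding.** Let c be the within-arm correlation between baseline outcome and mediator slope. The documents do not give it. With unit variances the unadjusted mediator path is biased by r × c. Simulation with no true mediator effect, r = .5, d = .72, N = 78:

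| c | Bias (.5 × c) | False positives, mediator path, unadjusted | Adjusted for Y0 | Sobel rejections, unadjusted | Sobel rejections, adjusted |
|---|---|---|---|---|---|
| 0 | 0 | 5% | 5% | 2% | 2% |
| -.1 | -.05 | 7% | 5% | 2% | 2% |
| -.2 | -.10 | 15% | 5% | 5% | 2% |
| -.3 | -.15 | 27% | 5% | 12% | 2% |

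The sign of c matters. With a true path of .39, c = -.2 shrinks the unadjusted estimate to about .29 and Sobel power to 41%, against 74% adjusted. With c = +.2 the unadjusted estimate rises to about .49.

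**6. Adding the baseline mediator as well.** With equal variances and r = .5, a change score correlates (r − 1)/√(2(1 − r)) = -.5 with its own baseline. If the baseline mediator has no effect of its own on the outcome, the SE with both baselines is √(.75/(.75 × 73)) = .117, so the gain in step 3 disappears. Sobel power still rises (about .55 to .66 and .67 to .75), because the arm-to-mediator path becomes more precise.

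**The case against.** **The regressor line may only name the exposure.** H1b also lists treatment group alone and then keeps the option of covariates, and Aim 3 lists it alone for models that contain time. The cited regression strategy may allow covariates, and some text around the baseline checks is missing from the available copy. This stands in part: the list does not prove that covariates are excluded. But the H2 text prespecifies none, and the visible lead-in to the gap concerns group differences only.

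**The plan already promises to account for differences.** That promise depends on imbalance between arms. It does not reach confounding within arms.

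**Confounding is not shown.** This stands. A reader might infer that baseline level is a known confounder and that H2 will yield spurious mediation. The documents give no correlation between baseline outcome and mediator slope; at zero there is no bias. The precision figures in step 3 contain no confounding at all. A false positive on the mediator path is also only one of the four conditions, and Sobel rejections are rarer (step 5).

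**The power gains are conditional.** This also stands. A reader might take .64 or .73 as the chance of declaring mediation under the plan. It is not; step 4 shows a much lower figure with or without the change. Nor does the fall in SE to .101 carry over to a model that also adds the baseline mediator.

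**Conclusion.** The point holds in limited form. H2 models week-15 levels of UPSA-B and WHODAS 2.0 without a prespecified baseline term, although the hypothesis concerns improvement and the baselines are collected.

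The 25% reduction in residual variance rests on one assumption, that the plan's .5 correlation applies from baseline to week 15. The SE and Sobel figures rest on assumed path values and on baseline being unrelated to the slope. The 5% to 27% range rests on an assumed correlation of 0 to -.3. Confounding is therefore potential, of unknown size and direction.

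A reader might extend this to housing, work or school, and appointment attendance. The documents do not support that: these outcomes have no identical baseline measure, and no gain has been computed for them.

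H2 is a mechanism aim, not the co-primary test, so this should be corrected but does not threaten the main result.

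**What to change.** In the H2 statistical analyses, prespecify the baseline value of the same outcome as a covariate in every regression for UPSA-B and WHODAS 2.0: the mediator model, the outcome model and the total-effect model. Apply it whether or not the arms differ at baseline.

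Baseline GDS or CPSA may be added to limit confounding and regression to the mean; participants enter with at least one domain T-score below 40. The SAP should give that reason and not promise a narrower standard error for the mediator path.

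State that other mediator-outcome confounding may remain after adjustment. Leave the models for the three 1-year proportions outside this change.

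The cost is SAP wording. No new data or visits are needed.

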as Random Regression Modeling and Hierarchical Linear Modeling) which takes advantage of all existing data points for minimal loss of data, will be used to analyze the data related to our main hypothesis (H1a). Therefore, we will not impute missing data because our analytic method uses all existing data points, including all subjects with missing data or those who were terminated early in the study, without relying on data imputation procedures (Diggle et al., 1994; Laird & Ware, 1982; Hedeker et al., 1991). The mixed effects approach provides more information and, therefore, more power compared to cross-sectional analyses that focus on the analysis of one summary index or more traditional analytic approaches such as a change score, end-point, or repeated measures analysis of variance (ANOVA). We will also use pattern-mixture models to assess if there is bias due to drop out or missing data. As described by Hedeker and Gibbons (1997), these mixed models allow us to assess whether important estimates are dependent on missing data patterns, and provide overall estimates of effects by averaging over the various missing-data patterns. In addition, we will consider the extension of the Pattern-Mixture models as described by Guo et al. (2004), which includes the incorporation of random effects in the pattern mixture model, allowing subject-to-subject heterogeneity. Missing data will be examined to assess randomness. The pattern of missing data will be examined according to the procedure recommended by Little and Rubin (1987), which includes comparing group differences in the primary outcomes of subjects with versus without missing data. SPSS and SAS statistical software will be used to analyze the data. Type I error will be controlled by a Bonferroni adjustment to the alpha per outcome domain for Hypotheses 1a and 1b. Specific plans for testing each hypothesis are below.

H1a: Positive CCT-associated effects on cognition, functional capacity (co-primary outcomes), and disability will emerge over the 15-week study.

Dependent variables: Cognition (global deficit score [GDS] composite; Heaton, et al., 1995), UPSA-B (co-primary outcomes), WHODAS 2.0.

Independent variables: Treatment group (CCT vs education control) and Time (0, 5, 10, 15 weeks).

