Statistical analyses: We will analyze data on all randomized subjects with a baseline assessment and at least one post-baseline evaluation, using mixed effects models, described above. The mixed effects model method provides an estimate of the individual variability around the population trend, the variability of the individual intercepts (baseline values) and slopes (changes across time), and the correlation between them. A fully saturated treatment by time model will be utilized for inference. Covariance structure will be chosen based on Akaike's Information Criterion (AIC). Random group level treatment effects will also be evaluated for importance based on the model AIC. This method allows for any group level effects to be incorporated into the model. Denominator degrees of freedom will be calculated using the Kenward-Roger small sample correction.

Power Analysis: We used procedures described by Hedeker et al. (1999) for Random Regression Models for the proposed study to estimate needed sample size (the RMASS program provided by Hedeker). We estimated that with a final sample size of 78 (target n=98, with a drop-out rate of 20%), the study will have .80 power to yield a statistically significant result for a .72 effect size, accounting for Type I error correction, .5 correlation between time points, and one random effect in the model. We have previously found CCT-associated effect sizes of .72 for prospective memory functioning in Veterans with mild to moderate TBI (74% of whom had PTSD), as well as for the UPSA-B in individuals with severe mental illness. Although we have not previously used the WHODAS 2.0 to assess disability, we have also found CCT-associated effect sizes of .81-1.0 for quality of life in these populations. The trial was therefore powered to detect effect sizes in the .72 range.

H1b: Positive CCT-associated effects on community reintegration outcomes (housing stability, participation in employment/education, healthcare appointment attendance) will be detected at the end of the 1-year follow-up.

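### The H2 mediation tests on UPSA-B and WHODAS 2.0 rest on a single week-15 score with no missing-data rule, so by default they use only Veterans seen at week 15

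*Combined protocol and SAP*

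**What the plan says.** All of this is in Section 9, Analytic Plan and Power Analyses.

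- **Imputation.** A mixed effects model "will be used to analyze the data related to our main hypothesis (H1a"). The next sentence draws the consequence: "we will not impute missing data because our analytic method uses all existing data points, including all subjects with missing data". Pattern-mixture models are planned as a check on dropout bias and are described as a form of the mixed models.
- **H1a analysis set.** "We will analyze data on all randomized subjects with a baseline assessment and at least one post-baseline evaluation, using mixed effects models".
- **H2 outcomes.** "UPSA-B at 15 weeks, WHODAS 2.0 at 15 weeks, proportion of months housed", then the proportions of months in work or school and of appointments attended.
- **H2 mediators.** "Cognitive improvement in GDS composite from 0-10 weeks (slope of change across weeks"), and the same for cognitive strategy use on the CPSA.
- **H2 method.** "For this hypothesis, we will use the regression analytic strategy described by" two cited mediation papers, with four conditions and a Sobel test. The first condition, (a), is "a significant relationship between the independent variable (treatment group) and the dependent variables listed above".
- **Missing data in the community outcomes.** Housing and work/school use the available months. Appointment attendance is said not to be subject to missing data.

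H2 has no stated analysis set, no rule for a missing week-15 UPSA-B or WHODAS 2.0, and no rule for computing a 0-10 week slope when a visit is missed.

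**The concern.** For H1a, the argument for doing without imputation is sound: a likelihood-based mixed model uses the earlier visits of a Veteran who leaves. That argument does not carry over to a regression on one week-15 value. A Veteran seen at weeks 0, 5 and 10 who then leaves has no outcome for the UPSA-B and WHODAS 2.0 mediation tests, and no other provision brings that Veteran in.

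Missing week-15 scores are expected. The plan budgets 20% attrition, and the average stay is given as 3 to 6 months, while week 15 falls at about 3.5 months.

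At stake is Aim 2. Its UPSA-B and WHODAS 2.0 results would describe a group selected after randomisation. The condition (a) effect could also differ from the H1a effect on the same outcome only because leavers were removed. The plan itself prefers the mixed model to end-point analyses.

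**Working it through.** **1. How many are affected.** Inputs from Retention and the H1a power paragraph: 98 randomised, 20% attrition, 78 remaining (39 per group).

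- 98 × 0.80 = 78.4, so 78. The plan's figure reproduces.
- 98 − 78 = 20 Veterans without a week-15 score.
- Cross-check that 78 is the plan's working sample: H1b claims .80 power for d = .64 at 39 per group. .64 × √(39/2) = 2.83, and Φ(2.83 − 1.96) = .807. This matches at two-sided .05.

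**2. Effect on condition (a).** The documents do not describe the dropout mechanism, so this is an illustration. Assumptions: scores with SD 1, correlation .5 between visits, true week-15 effect .72 (the plan's design effect), 20% dropout after week 10, and a logistic dropout model on the week-10 score (coefficient ±1 on the deviation from the arm mean).

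| Dropout pattern | Completers only | Using all visits |
|---|---|---|
| Random | .72 | .72 |
| Low scorers leave, both arms alike | .72 | .72 |
| Low scorers leave in control; random in CCT | .63 | .72 |
| Low scorers leave in control; high scorers in CCT | .55 | .72 |

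With stronger dependence on the score, the arm-dependent patterns reach about .50. If one dropout rule on the raw score applies to both arms, the result is about .69 to .70. The small shortfall arises because the arms then have different scores under the same rule.

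**3. Effect on the indirect effect.** H2 tests the product of two paths: a (treatment to mediator) and b (mediator to outcome, given treatment). Further assumptions: a = .6 and b = .39, so a × b = .6 × .39 = .234, with the total effect kept at .72. Dropout is about 20%, driven by the week-10 outcome score, with logistic coefficients of 1 to 1.5.

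| Who is used | a × b | Shortfall from .234 |
|---|---|---|
| Path a from everyone with mediator data, path b from completers (all patterns) | .223 to .232 | 1 − .232/.234 = 1% to 1 − .223/.234 = 5% |
| Both paths from completers (arm-dependent dropout) | about .18 to .21 | about 12% to 22% |
| Imputation from arm and all visits | about .234 | none material |

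Imputation also returned a total effect of .72 throughout. The size of the bias in a × b therefore depends on which Veterans enter path a, and the plan does not say.

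**4. Precision.** The H2 power paragraph claims 80% but states neither N nor path values. For scale only, with assumed standardised paths a = b = .39 and two-sided .05, a simulated Sobel test has about 85-86% power with 98 Veterans and 70-71% with 78. The figure for 98 is a ceiling: imputation recovers part of the gap, not all of it.

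The visit weeks are those of the Analytic Plan (0, 5, 10, 15). The Procedure section gives 3, 12 and 15 for the later visits; the argument does not depend on which is used.

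**The case against.** **The plan does not contradict itself.** A reader might infer that it promises to use all data and then breaks the promise in H2. The text does not support that: the no-imputation sentence follows directly from the choice of mixed model for H1a. This point stands. The defect is a gap, not a false statement.

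**Complete-case analysis is not stated.** The plan cites a regression strategy and never says that Veterans without a week-15 score are dropped. That is correct, but a regression on one value, with imputation ruled out and no alternative named, leads there by default.

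**Mediation is less exposed than the treatment effect.** A reader might take the fall from .72 to about .50 as the bias in the mediated effect. It is not; it concerns condition (a). The product a × b moves much less, and little at all if path a uses everyone with mediator data. This stands and sets the size of the point.

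**Material bias in the treatment effect needs dropout that differs by arm.** The documents give no positive reason to expect it: the control is matched for therapist time and attention, and participants live on site. This stands too. The scenarios also place all dropout after week 10, where earlier visits help most.

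**Slope precision.** A reader might infer that a slope from weeks 0-5 has four times the error variance of a 0-10 week slope and is nevertheless treated as equally precise. The factor (2s²/25 against 2s²/100) holds for a separate least-squares slope per person. The plan names no estimator, and slopes predicted from its mixed model would be shrunk for short series. Only the missing rule can be criticised.

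**Other checks.** The plan will compare participants with and without missing data on the primary outcomes, which include UPSA-B. That is a diagnostic and does not repair the H2 estimate.

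**Conclusion.** The point holds as a gap in a secondary, mechanistic aim. For UPSA-B and WHODAS 2.0, H2 as written uses about 78 of 98 randomised Veterans and leaves the week-5 and week-10 outcome scores of the others unused.

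Under the assumptions above, arm-dependent dropout takes the condition (a) effect to about .50 to .63 against .72. The indirect effect falls by 1-5%, or by 12-22% if all paths use completers. The fall would be larger (a × b of .06 to .17) if all paths use completers and dropout tracks the mediator itself differently by arm. If the dropout rule is the same in both arms, bias is small and the cost is mainly precision.

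The correlation of .5 and the effect of .72 are the plan's own planning values. The path sizes and dropout models are assumptions. The three community outcomes do not need a week-15 visit, so they are touched only through the unspecified slope calculation. Nothing here affects H1a, and the documents do not allow a finding that H2 is underpowered, because its N and paths are not given.

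**What to change.** Keep the planned regression and Sobel test, with mediators over weeks 0-10 and the outcome at week 15, and add to the H2 paragraph:

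1. The analysis set is all randomised Veterans, and it is the same for every mediation path.
2. Missing UPSA-B, WHODAS 2.0, GDS and CPSA values are multiply imputed. The imputation model includes arm and all observed visits (0, 5, 10, 15).
3. The 0-10 week mediator slopes are computed within each imputed data set, by a named estimator.
4. Complete-case results are reported as a sensitivity analysis.
5. The no-imputation sentence is expressly limited to H1a.

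A joint growth model of mediator and outcome is another option. It would let mediator and outcome overlap in time, and so would change what H2 estimates; imputation keeps the planned ordering.

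The cost is a few sentences and modest extra programming in SAS, with no new data. The analysis would rely on data being missing at random given the observed visits, and Veterans with no post-baseline data would add little.

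### The Sobel test planned for H2 is conservative at about 78 Veterans and misses mediation that a product-based interval would detect, and the percentage mediated is imprecise

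*Combined protocol and SAP*

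**What the plan says.** All of this is in the combined protocol and SAP, Section 9, Analytic Plan and Power Analyses.

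- **Gate.** H2 follows a regression strategy: "In this approach, four conditions must be met: a) a significant relationship between the independent variable (treatment group) and the dependent variables listed above". The other conditions are (b) treatment to mediator, (c) mediator to outcome, and (d) a significant drop in the treatment effect once the mediator is controlled.
- **Test.** "To test for significant mediation, we will conduct a Sobel test".
- **Summary.** A formula will be used to "determine the percentage of the intervention condition to primary outcome path that was accounted for by change in the mediator". No interval is planned for this percentage or for the indirect effect.
- **Scope.** Two mediators (GDS slope and CPSA slope, weeks 0 to 10) are crossed with five outcomes. The Bonferroni rule is stated for H1a and H1b only.
- **Power.** For H2, "we have assumed a medium effect for the relationships between intervention condition and dependent variables and between mediators and our primary outcome", and "we estimate that the proposed sample size would be sufficient to achieve 80% power to detect a mediated effect". The plan gives no numerical paths, no treatment-to-mediator effect, no alpha and no sidedness. It does not say whether the sample meant is 98 or 78.

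**The concern.** The Sobel test divides the product of two estimated paths by a standard error and refers the ratio to the normal distribution. In a small sample the product is skewed and the ratio is not standard normal, so the test rejects too seldom. Aim 2 asks how CCT works, and an over-conservative test can return no evidence of mediation when mediation exists. The percentage mediated has the estimated total effect as its denominator. When that effect is imprecise, a single reported percentage looks far more exact than the data allow.

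**Working it through.** **Inputs.** From the documents: 98 randomised with 20% attrition, so 98 × .80 = 78.4, about 78 (39 per group); design effects of .72 (H1a) and .64 (H1b). Assumed, because the plan is silent: H2 tested at two-sided .05, unit within-arm SDs, one mediator at a time, and the path values. Below, a is the treatment-to-mediator path in SD units and b is the mediator-to-outcome path adjusted for treatment.

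**The plan's own figures.** H1b: .64 × √(39/2) = 2.83, and Φ(2.83 − 1.96) = .81 (.797 with the t distribution), so that power figure reproduces. The 80% for H2 cannot be uniquely reproduced without path values. Two-sided Sobel power at 78 is .35 for a = .5, b = .39; .65 for a = .72, b = .39; and .70 for standardised paths of .39 and .39. At 98 the last two become .82 and .85.

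**Why the size is low.** Writing z_a = a/SE_a and z_b = b/SE_b, the Sobel statistic is

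z = ab / √(a²SE_b² + b²SE_a²) = z_a z_b / √(z_a² + z_b²).

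It is always smaller than either path's own z. With 39 per group, SE_a = √(2/39) = .226, so a = .72 gives z_a = 3.18. For |z| > 1.96 we need 1/z_b² < 1/1.96² − 1/3.18² = .260 − .099 = .161, that is |z_b| > 2.49. If b is truly 0 the chance of this is about .013. Simulation, which lets z_a vary, agrees (n = 78, nominal .05):

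| Null | Sobel | Monte Carlo interval |
|---|---|---|
| a = .72, b = 0 | .015 to .017 | .040 to .044 |
| a = .5, b = 0 | .005 to .007 | .028 |
| a = 0, b = .39 | .016 to .017 | .048 |

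**Cost in power.** Take a = .72, b = .3. SE_b is about √(.91/76) = .109, so z_b = 2.74 and z = 3.18 × 2.74 / √(10.11 + 7.51) = 2.08. Two paths that are each clearly significant give a borderline Sobel result. The last two columns of the next table also require a significant total effect, a path and b path, with the total effect set equal to a. The Sobel test (or the interval) stands in for condition (d).

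| a, b | Sobel alone | Interval alone | Gate + Sobel | Gate + interval |
|---|---|---|---|---|
| .5, .3 | .23 | .46 | .17 | .29 |
| .72, .3 | .49 | .69 | .44 | .61 |
| .72, .5 | .84 | .88 | .77 | .80 |

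These are simulation values and move by a few hundredths between runs and SD scalings; .46 is the least stable (.38 to .46). The direction does not change. A percentile bootstrap behaves similarly: .81 against .65 for Sobel at a = .72, b = .39.

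**Percentage mediated = ab / total effect.** The total effect has SE of about .226, so its 95% sampling range is ± .44: .20 to 1.08 around .64, .28 to 1.16 around .72, and .06 to .94 around .5. Dividing by a quantity that variable gives:

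- True share 30% to 50%, total effect .64 to .72 SD: about 6% to 110%, and up to 130% in one setting (true 39%, total .64, unit residual SDs).
- True 39%, total effect .5 SD: −6% to 188%.
- Among trials that declare mediation: about 21% to 93%. A true 30% then has a median estimate of about 40%; a true 39%, about 42% to 44%.

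**The case against.** Five points on the other side have force.

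1. **The plan does not run Sobel alone.** The gate requires three significant paths first, and comparing bare tests overstates the gain. This stands: with the gate kept, the gain is about .03 to .17 rather than .04 to .23. The significant total-effect condition can cost as much as the Sobel test or more. Under complete mediation with standardised paths of .39, meeting all conditions has probability .18, against .70 for Sobel alone.
2. **The error is conservative.** This stands. A reader might infer that H2 findings would be unreliable or falsely positive. They would not be; the loss is missed mediation in a mechanistic aim, and H1a and H1b are untouched.
3. **Low size is not universal.** This stands. With b = .59 and a = 0 the Sobel size is .033, and with a very large standardised path about .044. When both paths are null, the bootstrap is also far below nominal (.4%).
4. **The percentage is rarely absurd when it matters.** A reader might infer that it will often fall below 0% or above 100%. That holds for small total effects without conditioning. Once mediation is declared, only about 1% of estimates do so. The text does not, however, limit reporting to those cases.
5. **A less conservative test has a price.** With the gate kept, per-test false positives rise from about .015 to .038 (a = .72, b = 0), across 2 × 5 = 10 uncorrected tests. It would be wrong to call the change free of error cost.

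A reader might also infer that the plan reports an incorrect symmetric interval. It plans no interval at all.

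**Conclusion.** The point holds in a limited form. At about 78 Veterans the Sobel test runs at roughly .005 to .02 instead of .05 when one path is null and the other medium to moderately large. Replacing it recovers about .03 to .17 in the chance of declaring mediation under the plan's own path-significance conditions. The percentage mediated is too imprecise to report as a bare number, and it is biased upward when the true share is small and mediation has been declared.

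The sizes rest on assumed paths, alpha and sidedness and on a single-mediator linear model. It is tempting to conclude that the 80% power claim for H2 is wrong. The documents do not support that: it is not reached at 78, two-sided, in the medium scenarios tried, but it is reached in some of them at 98 or with a one-sided test, and the plan does not say which was meant. This should be changed, but it does not threaten the primary analysis.

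**What to change.** In the H2 statistical analyses:

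- Replace the Sobel test with a 95% Monte Carlo (distribution-of-product) or percentile-bootstrap interval for a × b, and conclude mediation when it excludes 0.
- State that this interval takes the place of both the Sobel test and condition (d), and say explicitly whether the significant total-effect condition (a) is kept.
- Report a × b in outcome units with its interval. Drop the percentage, or give it only with an interval.
- Label H2 results as not adjusted for multiplicity across the ten mediator-outcome pairs.
- State the a and b values, alpha, sidedness and sample size behind the 80% power figure, and recompute it for the new procedure.

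The cost is a few sentences and a standard routine, with no new data, visits or participants. The downside is that per-test false positives rise towards, but not materially above, about .05, which is why the multiplicity label is needed.
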